10.2.4. Reporting of SAE to GSK

SAE Reporting to GSK via Electronic Data Collection Tool

- The primary mechanism for reporting SAE to GSK will be the electronic data collection tool.
- If the electronic system is unavailable, then the site will use the paper SAE data collection tool (see next section) in order to report the event within 24 hours.
- The site will enter the SAE data into the electronic system as soon as it becomes available.
- The investigator or medically-qualified sub-investigator must show evidence within the eCRF (e.g., check review box, signature, etc.) of review and verification of the relationship of each SAE to study participation (causality) within 72 hours of SAE entry into the eCRF.
- After the study is completed at a given site, the electronic data collection tool will be taken off-line to prevent the entry of new data or changes to existing data.
- If a site receives a report of a new SAE from a study participant or receives updated data on a previously reported SAE after the electronic data collection tool has been taken off-line, then the site can report this information on a paper SAE form (see next section) or to the medical monitor/SAE coordinator by telephone.
- Contacts for SAE reporting can be found in the SRM.

SAE Reporting to GSK via Paper CRF

- Facsimile transmission of the SAE paper CRF could be an alternative method to transmit this information to the **medical monitor or the SAE coordinator** if eCRF is not available.
- In rare circumstances and in the absence of facsimile equipment, notification by telephone is acceptable with a copy of the SAE data collection tool sent by overnight mail or courier service.
- Initial notification via telephone does not replace the need for the investigator to complete and sign the SAE CRF pages within the designated reporting time frames.
- Contacts for SAE reporting can be found in the SRM.

10.3. Appendix 3: Abbreviations and Trademarks

ACT	Adoptive Cell Therapy
AE	Adverse event
CAR	Chimeric Antigen Receptor
CAR-T	Chimeric Antigen Receptor -T cell
CFR	Code of Federal Regulation
CIOMS	Council for International Organizations of Medical Sciences
CONSORT	Consolidated Standards of Reporting Trials
CRF	Case Report Form
CSR	Clinical study report
СТА	Cancer testis antigens
ctDNA	Circulating tumor DNA
CV	Cardiovascular
DLBCL	Diffuse Large B-cell Lymphoma
DNA	Deoxyribonucleic acid
DOR	Duration of response
eCRF	Electronic case report form
ECG	Electrocardiogram
ECOG	Eastern Cooperative Oncology Group
GCP	Good Clinical Practice
GSK	GlaxoSmithKline
HIPAA	Health Insurance Portability and Accountability Act
HLA	Human Leukocyte Antigen
IB	Investigator's Brochure
ICF	Informed Consent Form
ICH	International Council of Harmonization
IEC	Independent Ethics Committee
IRB	Institutional Review Board
LAGE-1a	Tumour antigen, cancer-testis antigen family
MedDRA	Medical Dictionary for Regulatory Activities
MHC	Major histocompatibility complex
mL	Milliliter
MRCLS	Myxoid/round cell liposarcoma
NSCLC	Non-small cell lung cancer
NY-ESO-1	New-York Esophageal Antigen-1
ORR	Overall Response rate
RAP	Reporting and Analysis Plan
SAE	Serious adverse event
SOA	Schedule of Activities
SOP	Standard Operating Procedure
SRM	Study reference manual
SUSAR	Suspected unexpected serious adverse reaction
TAA	Tumor-associated antigen
TCR T	T-cell Receptor-targeting

Trademark Information

Trademarks of the GlaxoSmithKline
group of companies

None

Trademarks not owned by the GlaxoSmithKline group of companies

MeDRA

TMF-13837201 CONFIDENTIAL

1. INTRODUCTION

The purpose of this SAP is to describe the planned final analyses for Study 213033. Due to the lack of enrolment and poor site engagement, the study has been terminated early. The analyses specified in this plan is to support the synoptic CSR only.

1.1. Objectives, Estimands and Endpoints

Estimands are not applicable for this study.

Objectives	Endpoints
Primary (Operational)	

Determine germline HLA genotype of all enrolled participants.	
Prevalence of HLA-A*02:01, HLAA* 02:05, or HLA-A*02:06 allele subtypes

[1] MRCLS: Myxoid/round cell liposarcoma

2. STATISTICAL HYPOTHESES

This is a screening protocol. The analysis will be descriptive in nature. No formal hypothesis will be tested under this protocol.

2.1. Multiplicity Adjustment

No formal statistical testing will be performed; therefore, no adjustments for multiple comparisons or multiplicity are planned.

3. ANALYSIS SETS

Analysis Set	Definition / Criteria	Analyses Evaluated
Screened	
 • All participants who sign the ICF 	
 • Study Population
Enrolled	
 • All participants who provide sample for biomarker assessment 	
 • Study Population • Safety

4. STATISTICAL ANALYSES

4.1. General Considerations

Unless and otherwise specified, indications tumour type will be used as table columns. Total column will be reported if more than one indication is reported.

4.1.1. General Methodology

Unless otherwise specified, continuous data will be summarized using descriptive statistics: n, mean, standard deviation (std), median, minimum and maximum. Categorical data will be summarized as the number and percentage of participants in each category.

4.1.2. Baseline Definition

Unless and otherwise specified visit 1 assessments (screening visit) will be considered as baseline for demographics displays.

Unless otherwise stated, if baseline data is missing no derivation will be performed and baseline will be set to missing.

4.2. Primary Endpoint(s) Analyses

4.2.1. Definition of endpoint(s)

Prevalence of HLA-A*02:01, HLAA* 02:05, or HLA-A*02:06 allele subtypes.

4.2.2. Main analytical approach

“Enrolled” analysis set will be used to perform primary endpoint analysis.

[figure not shown]
A summary of participant’s HLA A genotype status will be provided. This summary contains the number and percentage of participants in each of the allele sub-types (HLA A genotypes).

A subject level listing containing allele subtypes and tumour types will also be provided.

4.3. Secondary Endpoint(s) Analyses

There are no secondary endpoints defined under this protocol. Hence, this section is not applicable.

CCI

4.5. Safety Analyses

The safety analyses will be based on the “Enrolled” Analysis Set, unless otherwise specified.

Only AEs which lead to study withdrawal, as determined, and collected in eCRF by the investigator are collected in this study. If there are no AEs/SAEs in the database, a standard ‘No data to report’ display will be generated.

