9.4. Statistical Analyses

9.4.1. Safety Analyses

All safety analyses will be performed on all patients who provided informed consent.

Data will be listed and summarized according to the GSK reporting standards, where applicable. Complete details will be documented in the Reporting and Analysis Plan (RAP). Any deviations from, or additions to, the original analysis plan described in this protocol will be documented in the RAP and final study report.

SAE data will be summarized overall; by tumor type; and by HLA subtype. These summaries will be categorized by frequency and proportion of total subjects. All SAEs will be coded using the standard Medical Dictionary for Regulatory Activities (MeDRA). Summary of AEs leading to study withdrawal will also be provided.

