4.5.2. Adverse Events/Serious Adverse Events

Adverse events analyses including the analysis of adverse events (AEs), serious adverse events (SAEs) will be based on GSK Core Data Standards. Adverse events will be coded using the standard Medical Dictionary for Regulatory Affairs (MedDRA dictionary) and grouped by system organ class (SOC) and preferred term (PT). Adverse events will be graded by the investigator according to the National Cancer Institute Common Terminology Criteria for Adverse Events (NCI-CTCAE v 5.0).

An overview summary of AEs, including counts and percentages of participants with any AE will be created by SOC and PT.

All SAEs will be tabulated based on the number and percentage of participants who experienced the event by SOC and PT. The summary of all SAEs will be created by SOC and PT.

A summary of fatal SAEs will also be provided.

A summary of Non-serious AEs and Fatal SAEs will also be provided by SOC and PT.

A listing of all AEs collected will be provided. SAE flags are included in the listing of all AEs. Separate supportive listings with participant level details will be generated for

- Fatal SAEs
- Non-Fatal SAEs.

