4.7. Changes to Protocol Defined Analyses

There were no changes or deviations to the originally planned statistical analysis specified in the protocol (Dated: 22-JUN-2021).

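### The SAP narrows the safety population from all consenters to sample providers and omits the SAE breakdown by HLA subtype, yet declares no change from the protocol

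*SAP*

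**What the plan says.** Protocol section 9.4.1 fixes the safety population: "All safety analyses will be performed on all patients who provided informed consent". This is the Screened population of Protocol section 9.3. The same section sets the SAE displays: "SAE data will be summarized overall; by tumor type; and by HLA subtype". It also sets a rule for departures: "Any deviations from, or additions to, the original analysis plan described in this protocol will be documented in the RAP and final study report".

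The SAP reads differently. Section 4.5 says: "The safety analyses will be based on the “Enrolled” Analysis Set, unless otherwise specified". Section 3 defines Enrolled as "All participants who provide sample for biomarker assessment", and its table assigns safety to Enrolled only; Screened is assigned to study population displays alone. Section 4.1 makes tumor type the default column layout ("indications tumour type will be used as table columns"), with a total column when there is more than one indication. Section 4.5.2 breaks AEs and SAEs down by system organ class and preferred term and does not mention HLA. Section 4.7 then states: "There were no changes or deviations to the originally planned statistical analysis specified in the protocol".

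**The concern.** The two documents name different safety populations and different sets of SAE displays, and the SAP says there is no difference.

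The population change is more than a label. Protocol section 8.4.1 collects procedure-related SAEs, and AEs and SAEs leading to withdrawal, from signature of the consent form through to completion, withdrawal or screen failure. Consenters without a sample can exist: Protocol section 7.2 counts failure to give the sample as early withdrawal, and SAP section 6.1.1 plans a listing of people who are in the Screened set but not in Enrolled. If one of them withdraws because of an AE or SAE, the event is reportable under the protocol but missing from the SAP's summary tables.

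Two things are at stake. Withdrawal-causing events are one of the two kinds of safety event the protocol collects, and those occurring before the draw would not be counted. The report would also state that the analysis followed the protocol when two specified elements did not.

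**Working it through.** The plan has no figure to reproduce: the study is descriptive and the planned size of about 1000 plays no part here. The check is a comparison of texts.

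| Element | Protocol 9.4.1 | SAP | Same? |
|---|---|---|---|
| Safety population | All who consented (Screened) | Sample providers (Enrolled), sections 3 and 4.5 | No |
| SAEs overall | Required | Total column, section 4.1 | Yes |
| SAEs per tumor type | Required | Default columns, section 4.1 | Yes |
| SAEs per HLA subtype | Required | None in section 4.5.2 | No |
| Departures documented | Required | Section 4.7: none | No |

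**Can another SAP clause remove the conflict?** Section 4.5 allows exceptions to its default, but no readable safety display is assigned to Screened, and that includes the deaths listing in section 4.5.3.1. Screened is used only for disposition and screen-failure displays. In the readable SAP, HLA appears only under the primary endpoint. Some SAP text is blacked out after sections 4.3 and 6.1.1, but sections 4.5 and 4.5.2, where SAE displays belong, show no redaction.

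**Counts.**
- AE/SAE summaries under the Enrolled default: AE overview, all SAEs, fatal SAEs, non-serious AEs with fatal SAEs = 4.
- Required SAE breakdowns: 3. Provided: 2. Missing: 3 − 2 = 1.
- Departures: population + HLA display = 2. Declared in section 4.7: 0.

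**Effect of the population change.** Let s be the number consented and u the number of those without a sample.
- Protocol denominator: s. SAP denominator: s − u.
- Participants with a reportable event left out of the four summaries: at least 0, at most u.
- If u = 0, the two sets coincide and nothing changes.
- If u > 0 and none of the u had an event, only the denominator changes.

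The documents give neither s nor u, so no numerical estimate is possible.

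**Which events are exposed?** The population change does not touch an SAE caused by a draw that yields a sample, because that participant is Enrolled. The exposed events are those in people who leave before sampling or whose draw yields no sample.

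**The case against.** The strongest reply is that little turns on this. There is no study drug, consent and blood draw both belong to Visit 1, enrolment was limited, and the SAP supports a synoptic report only. The number affected may be zero. All of that stands, and it limits the importance of the point. Electronic consent with later sampling (Protocol section 10.1.3) could widen the gap between consent and draw, but nothing shows that it was used.

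Events may also survive in listings: "A listing of all AEs collected will be provided", says SAP section 4.5.2, and unsampled consenters appear in the section 6.1.1 listing. This stands in part. The AE listing sits under a section whose default is Enrolled, so its coverage is unclear, and a listing does not correct the counts in a summary table.

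The protocol synopsis ties the safety assessment to people who gave a sample, which makes the SAP's choice understandable. But it describes who is assessed and does not define an analysis population; the statistical section does that explicitly.

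The reason in Protocol section 7.2 is separate from withdrawal for an AE. It shows that unsampled consenters can exist, not that any of them had an event. That is correct, and nothing here claims otherwise.

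Early termination could justify dropping a nearly empty HLA table. It could, but the SAP gives no such reason and section 4.7 denies any change.

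Finally, section 4.7 cites a protocol dated 22-JUN-2021, and that date cannot be matched to the supplied text because its title page was removed. This is a limit of the check.

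**Conclusion.** The concern holds. The SAP departs from Protocol section 9.4.1 in two respects, the safety population and the SAE display per HLA subtype, and section 4.7 declares neither. That statement is inaccurate whatever the data turn out to be.

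The numerical consequence lies between 0 and u participants with an event missing from four summaries, with u unknown and possibly zero. It is probably small. The point should be fixed because the fix is cheap and a false statement of no change would otherwise be carried into the report. The conclusion assumes that the supplied protocol is the version section 4.7 cites, and that the blacked-out SAP text holds no SAE display per HLA subtype and no reassignment of the safety set. The unredacted safety sections support the second assumption.

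**What to change.** Preferred: in SAP sections 3 and 4.5, make Screened the safety analysis set, with an Enrolled display as supportive if wanted. Restore the SAE display per HLA subtype with a category for participants not tested in this study, so that any earlier typing held in the eCRF is not mislabelled. Count rescreened people once: they receive a new identifier under Protocol section 10.1.3, and the once-only rule in SAP section 6.1.1 covers only its own displays.

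Alternative: keep Enrolled and omit the HLA display, but record both departures with reasons in section 4.7 and in the synoptic report, and list separately any AE or SAE in consenters without a sample.

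Either way, correct section 4.7 so that every departure kept is declared.

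The cost is SAP wording, a population flag in the AE programs and one data check before database freeze. Protocol section 5.4 names only procedure-related SAEs in the minimal data for screen failures, while section 8.4.1 also requires withdrawal-causing events. The sponsor should confirm that such events in unsampled consenters were entered. The sentence in SAP section 4.5 that limits collected AEs to those causing withdrawal should be aligned with section 8.4.1 at the same time, since read literally it leaves out procedure-related SAEs that did not lead to withdrawal.

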This protocol is designed to facilitate screening for HLA histocompatibility testing by blood sample analysis in participants diagnosed with various malignancies. This will support participant identification for referral into an appropriate GSK cell therapy investigational treatment trial. It is anticipated that this screening protocol will support clinical trials of lete-cel, next generation NY-ESO-1 TCR T-cell products (e.g. GSK3901961, GSK3845097, etc) and other GSK engineered T-cell assets, as these assets become available for clinical development, and additional tumor types as the investigational treatment master protocols expand and/or as other investigational treatment protocols are initiated.

Number of Participants:

Approximately 1000 participants will be enrolled in this screening study. The overall number of participants screened under this protocol will depend upon the recruitment progress on investigational treatment trials.

Procedures and Duration:

During study Visit 1, all participants who consent to the screening study and are determined to meet the eligibility criteria for Study 213033 will provide the mandatory screening samples. Participants who consent to the screening study are considered screened in the study. A blood sample for HLA compatibility testing will be collected.

TMF-13837201

Details of HLA compatibility testing and of sample management are provide in the SRM. Participants who provide blood sample for HLA compatibility testing are considered enrolled in the study.

If the participant is determined to have qualifying results for an intended investigational treatment protocol, then the participant may be considered for referral to GSK trial site to complete the rest of the eligibility assessments for the investigational treatment trial.

If a participant is referred to a GSK investigational treatment study, depending on the specific requirements of the investigational treatment protocol, the test result from this screening study may be used. Compatibility testing may however need to be repeated, either with the sample that was already provided as part of this screening study, or in rare cases a fresh sample may need to be collected under the investigational treatment study. All participants who have provided a sample for testing will undergo a safety assessment for any serious adverse events (SAEs) assessed as related to protocol-mandated study procedures or adverse events (AEs) leading to study withdrawal.

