1.3. Schedule of Activities (SoA) for Study 213033

[figure not shown]
Procedures	Visit 1	Visit 24	
Informed consent	X		Footnotes:
Inclusion and exclusion criteria	X		and surgeries will be collected for all enrolled Synovial Sarcoma / myxoid/round cell liposarcoma (MRCLS) participants; and will be recorded in the Screening eCRF.
Eatern Cooperative Oncology Group (ECOG) status	X		2.Human Leukocyte Antigen (HLA) sample – one blood sample (see Section 8.1). 3.If prior molecular HLA Class I typing HLA A results are available, record in the electronic case report
CCI			form (eCRF). Prior HLA result will not replace the HLA genotyping that is a mandatory part of this screening study. If patient is known to be positive for HLA 02:01, HLA A02:05 and/or HLA A02:06 then patient can be referred to an investigational site. 4.Visit 2 is Completion / Withdrawal and may occur remotely via tele health / phone visit
HLA genotyping ^{2,3}	Х		,
Review of serious adverse events (SAEs) that are related to study procedure(s) or adverse events (AEs) and SAEs that lead to study withdrawal	х	х	
Consider referral to an appropriate investigational treatment trial		х	

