8.3. Safety Assessments

All participants will be followed for all SAEs related to protocol-mandated procedure(s), and AEs or SAEs leading to withdrawal from the study.

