8.4.1. Time Period and Frequency for Collecting SAE Information

- All SAEs assessed as related to protocol-mandated procedure(s) or both AEs and SAEs leading to early study withdrawal (whether or not related to study procedures) will be collected from the signing of the informed consent form (ICF) until conclusion of study participation (completes study, withdraws early, or screen fails), at the time points specified in the SoA (Section 1.3).
- All SAEs assessed as related to protocol-mandated procedure(s) or leading to early study withdrawal (whether or not related to study procedures) will be recorded and reported to the sponsor or designee immediately and under no circumstance should this exceed 24 hours, as indicated in Appendix 2. The investigator will submit any updated SAE data to the sponsor within 24 hours of it being available.
- Investigators are not obligated to actively seek SAEs after the conclusion of the study participation. However, if the investigator learns of any SAE, including a death, at any time after a participant has been discharged from the study, and he/she considers the event to be reasonably related to a study procedure, the investigator must promptly notify the sponsor.

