Examples of such events include invasive or malignant cancers, intensive treatment in an emergency room or at home for allergic bronchospasm, blood dyscrasias or convulsions that do not result in hospitalization, or development of drug dependency or drug abuse.

All participants will be followed for all SAEs related to study procedures and for all SAEs leading to withdrawal from the study.

The investigator and any qualified designees are responsible for detecting, documenting, and reporting events that meet the definition of an SAE and remain responsible for following up SAEs that are considered related to the study procedure(s) or that caused the participant to withdraw early, whether or not related to study procedures (see Section 7).

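### Does SAP 4.5 leave procedure-related SAEs out of the safety reporting, and does SAP 4.5.2 drop the promised summary of AEs leading to withdrawal?

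*SAP*

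**What the plan says.** **Collection, per the protocol.** Section 8.3: "All participants will be followed for all SAEs related to protocol-mandated procedure(s), and AEs or SAEs leading to withdrawal from the study". Section 8.4.1 defines the collected set as "All SAEs assessed as related to protocol-mandated procedure(s) or both AEs and SAEs leading to early study withdrawal", from consent to the end of participation. The Schedule of Activities (1.3) has the same two classes reviewed at both visits. Procedure-related SAEs carry no withdrawal condition in any of these places.

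**Collection, per the SAP.** Section 4.5: "Only AEs which lead to study withdrawal, as determined, and collected in eCRF by the investigator are collected in this study". The next sentence provides for an empty display when the database holds neither AEs nor SAEs.

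**Outputs.** Protocol 9.4.1 promises SAE summaries and, in addition, a summary of AEs leading to study withdrawal. SAP 4.5.2 names four summaries (any AE; all SAEs; fatal SAEs; non-serious AEs together with fatal SAEs) and three listings (all AEs; fatal SAEs; non-fatal SAEs). On the fourth summary it says: "A summary of Non-serious AEs and Fatal SAEs will also be provided by SOC and PT". On the first listing: "SAE flags are included in the listing of all AEs". SAP 4.7 states that nothing departs from the analysis planned in the protocol.

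**The concern.** SAP 4.5.2 treats SAEs as flagged members of the AE listing. If the word AEs in SAP 4.5 is read the same way, the sentence says that an SAE caused by the blood draw is collected only if the participant withdraws. That contradicts the protocol, and it concerns the event class tied to specimen collection, which Protocol 2.3.1 calls the primary risk. An empty safety display would then leave a reader unsure whether procedure-related SAEs had been looked for at all.

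Separately, a summary promised in Protocol 9.4.1 has no counterpart by name in the SAP. Protocol 9.4.1 asks for deviations from its analysis plan to be documented, yet SAP 4.7 records none. At stake would be an accurate statement of what safety information was sought, and whether a reported non-fatal SAE led to withdrawal.

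**Working it through.** No figure in the plan is in dispute, so the check sets the texts side by side.

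**1. What the SAP sentence can mean.**
- *Non-serious AEs only.* It then agrees with the protocol, which collects a non-serious AE only when it leads to withdrawal. In support, the very next SAP sentence names AEs and SAEs separately, and SAP 4.5.2 tabulates all SAEs without restriction.
- *AEs including SAEs.* It then omits procedure-related SAEs without withdrawal. In support, there is the SAE flag in the listing of all AEs.

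The protocol's own usage does not settle it. Sections 8.3 and 8.4.1 name both when both are meant, but the synopsis writes "serious adverse events (SAEs) assessed as related to protocol-mandated study procedures or adverse events (AEs) leading to study withdrawal", where AEs must cover serious ones too if it is to match the rest. Section 10.2.2 mentions SAEs alone: "All participants will be followed for all SAEs related to study procedures and for all SAEs leading to withdrawal from the study".

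**2. What happens to the data on either reading.** The sentence describes collection, and sites collect under the protocol. A procedure-related SAE without withdrawal in an enrolled participant enters the any-AE summary, the all-SAE summary, the listing of all AEs and the relevant SAE listing. Nothing in SAP 4.5.2 filters on withdrawal.

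**3. Where the promised summary could be missing content.** Cross three types (non-serious AE, non-fatal SAE, fatal SAE) with procedure-related or not and withdrawal or not: 3 × 2 × 2 = 12 combinations. Apply the collection rules, counting death as early withdrawal as Protocol 7.2 does:

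| Type | Collected, with withdrawal | Collected, without withdrawal |
|---|---|---|
| Non-serious AE | 2 (related, unrelated) | 0 |
| Non-fatal SAE | 2 (related, unrelated) | 1 (related) |
| Fatal SAE | 2 (related, unrelated) | 0 |

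That gives 6 + 1 = 7 collected combinations, with a single one outside withdrawal. The table locates the ambiguity; it does not measure it, because the combinations carry no event counts.

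**4. The Protocol 9.4.1 summary on each reading.**
- If AEs there means non-serious AEs (the section deals with SAEs first and then adds this item), the non-serious AE and fatal SAE summary already holds the content.
- If it includes SAEs, the number of participants with a withdrawal event lies between the count in that summary and the any-AE count. The two counts differ only when some participant's collected events are all non-fatal SAEs.

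Hypothetical example: one participant withdraws because of a non-fatal SAE, and another has a procedure-related non-fatal SAE and stays. The any-AE summary shows 2, the non-serious and fatal summary shows 0, and the promised summary would show 1. No named table gives the 1, but both events are listed individually. SAP 6.1.1 also gives study disposition for the enrolled set if anyone withdraws.

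**The case for a change.** The best argument for acting is that some mismatch remains on either reading. If the SAP sentence covers SAEs, it conflicts with the protocol, although the any-AE summary is then in substance the promised one. If it covers non-serious AEs only, the conflict goes, but the any-AE summary can mix withdrawal and non-withdrawal events and cannot stand in for the promised summary. Disposition does not fully fill the gap: the withdrawal reasons in Protocol 7.2 have no separate entry for adverse events, and disposition carries no SOC or PT detail. The remedy would be cheap.

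Much of this stands as description: SAP 4.5 is imprecise, and SAP 4.7 could have recorded that the named summary was folded into other displays. What does not follow is a consequence. The second limb also needs AEs in Protocol 9.4.1 to include SAEs; otherwise an existing table answers it. Whether the listings show withdrawal cannot be judged, because their columns are not in the documents. The empty-display worry is weak too: that display is triggered by the absence of AEs and SAEs alike, and the protocol states what was sought.

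**Conclusion.** No change to the plan is called for. The scope sentence is loosely worded, and the missing title is a labelling gap that an analyst working with the protocol would fill sensibly. Followed as written, the SAP still tabulates and lists the AEs and SAEs collected from enrolled participants. The remaining ambiguity is confined to non-fatal SAEs: whether a given one led to withdrawal is not separated in the named tables. With limited enrolment (SAP 5), a single planned blood sample, no hypothesis test and a synoptic CSR as the only product (SAP 1), resolving it would alter no conclusion.

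This rests on four points. Sites collected under the protocol's rules. Event counts are not given and may be zero. Death is counted as withdrawal under Protocol 7.2, although 4.4.1 lists the two separately; a procedure-related death learned of after discharge (8.4.1) would be a fatal SAE without withdrawal, but would still appear in the fatal-SAE outputs if entered in the database. Finally, the conclusion covers only this point: the protocol bases safety analyses on all consenting participants and the SAP on those enrolled, which is a separate matter.
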